[figure not shown]
Research topics	Arthroscopic Assisted Balloon Tibioplasty for the Treatment of Schatzker II-IV Tibial Plateau Fractures
purpose	Objective to compare the clinical diagnosis and treatment of open reduction and internal fixation with Schatzker II-IV tibial plateau fracture or arthroscopic assisted balloon tibioplasty of tibial plateau fractures.
overall design	This study used a randomized controlled trial design research.
diagnostic criteria	At least 2 fixed researchers by X-ray or CT examination to determine fracture type
Screening criteria	
Inclusion criteria: The following criteria must be according with.
 
(1) fresh closed fracture, X-ray and CT examination diagnosed Schatzker type II-IV tibial plateau fracture patients(2) sign the informed consent form(3) age from 18 to 80 years 
Exclusion criteria:
 
(1) exclude open fractures, pathological fractures, immunodeficiency, hematological diseases and severe hepatorenal disorders(2) refuse to sign informed consent form

Methods	
Experimental group: patients were randomly divided into the experimental group and underwent Arthroscopic Assisted Balloon Tibioplasty.
 
Control group: patients were randomly divided into control group and underwent Open Reduction and Internal Fixation(ORIF).

Curative effect observation index	
Primary Outcome Measure:
 
1.Rasmussen scores change after surgery the knee joint Rasmussen scores change after surgery [Time Frame: 1、2、3、4、6、12mouth Rasmussen scores change after surgery]
 
Secondary Outcome Measures:
 
1.Intraoperative blood loss blood loss in surgery [Time Frame: Operation day]
 
2.Postoperative pain score Postoperative pain score(Visual Analogue score, range of scores from 0 to 10, the score is designed to measure the level of the pain and the higher score is, the more painful the patient is) [Time Frame: from operation day to leave hospital day(up to 2 weeks)]
 
3.Fracture healing time Fracture healing time [Time Frame: from leave hospital day to healing time(up to 1 year)]
 
4.The percentage of joint area recovered after operation was

	
satisfactory
 
The percentage of joint area recovered after operation was satisfactory
 
[Time Frame: 1、2、3、4、6、12 mouth after surgery]
 
5.operation time
 
Duration of surgery
 
[Time Frame: Operation day]
 
6.the postoperative hospital stay days
 
the total hospital stay days after surgery
 
[Time Frame: from operation day to Leave hospital day(up to 4 weeks)]

Safety observation index	Intraoperative vital signs, Intraoperative C arm examination, postoperative examination etc.
Visiting point	Screening / baseline: admission to the preoperative / postoperative day from the first day to the day of discharge. 1、2、3、4、6、12 mouths after the operation.
statistical analysis	Spss22.0 software was used for statistical analysis. The measurement data in SX, using t test, count data expressed as a percentage, using X - test, $P < 0.05$, the difference has statistical significance, and draw the relevant charts with RevMan software. Case characteristics and efficacy analysis were analyzed by complete analysis set (FAS) and compliance program set (PPS), and safety evaluation was analyzed by safety set (SS).
sample size	A total of 40 patients were included this project, the experimental group 20 cases and the control group 20 cases.
Research cycle	July 2017 ~ June 2020

Technology Roadmap

Technology Roadmap

Project text

1. Research topics

Arthroscopic Assisted Balloon Tibioplasty for the Treatment of Schatzker II-IV Tibial Plateau Fractures

2. Research background

Tibial plateau fractures account for 1-2% of all fractures, including 8% of the elderly. In recent years, the incidence of accidents such as traffic accidents and high falls has increased the incidence of tibial plateau fractures. The traditional internal fixation treatment has a series of demerits such as too much damage, the limited expansion of articular cavity, the insufficient diagnosis and treatment for the internal joint injury and the postoperative complications such as the infection of incisional wound and joint degeneration. In recent years, with the development of technology, the treatment concept of tibial plateau fractures has developed from original mechanical fixation to present biomechanical fixation and minimally invasive surgical direction, namely developed from the absolute anatomic reduction and fixation, fracture mechanics healing fixed to minimally invasive operation, indirect reduction and elastic fixation, indirect fracture healing (callus healing). Such as MIPPO technology represented by the LISS system, arthroscopic assisted reduction and internal fixation technology, as well as recently suggested balloon dilation tibioplasty (Balloon Tibioplasty) and other surgical techniques. The key of the Schatzker II-IV type of tibial plateau fracture treatment is to the medial and lateral tibial plateau collapse of the articular surface reduction, arthroscopically assisted balloon distension tibial plasty as an emerging technology, which aims to arthroscopy assisted by the ball Capsule expansion tibial angioplasty, reduction of the collapse of the articular surface, and according to the patient's specific injury to be plate fixation, the technology has shown its initial collapse of the articular surface reduction accuracy, and its surgical trauma is small, postoperative better functional recovery of the joint and early functional exercise of the patient. However, the short occurrence time, the high cost of operation, the unripe surgical technique and the lack of clinical promotion have also been reported in the literature both at home and abroad. Postoperative leakage of bone cement and fractures lost patients reset, the lack of long-term follow-up, and no large number of case data, the clinical treatment remains to be further observed and studied.

3. Test purpose and design basis

3.1 Purpose

Based on the current data of arthroscopically assisted balloon expansion tibial angioplasty, we designed the subject.1. For the patients who met the inclusion criteria, we randomly performed Open Reduction and Internal Fixation or Arthroscopically assisted balloon expansion tibia. Surgical follow-up, statistical evaluation of the two techniques after surgery for the tibial plateau joint resection and joint function recovery clinical efficacy difference. 2. Through the clinical practice and experience summary, found that the new technology in the operation of the deficiencies in order to improve the technology. 3 through the results of feedback and analysis to guide the clinical diagnosis and treatment.

3.2 Research overall design

The use of existing resources in our hospital to carry out this new technology for patients who meet the inclusion criteria, randomized performed traditional Open Reduction and Internal Fixation or Arthroscopically assisted balloon distension tibial angioplasty, access to a certain period of time the corresponding patient raw data, through professional statistics and epidemiological analysis of comparative data, analysis and discussion based on the analysis results and experience. Concluded the postoperative tibial plateau joint surface resection and joint function recovery clinical efficacy difference between the Balloon Tibioplasty and traditional Open Reduction and Internal Fixation, and the results of feedback to guide the clinical diagnosis and treatment. .

3.3 Sample size

A total of 40 patients were included this project, the experimental group 20 cases and the control group 20 cases.

3.4 Study patients

Outpatient and emergency patients in trauma department of orthopedics of our hospital.

4. Research subjects

4.1 inclusion criteria

- (1) fresh closed fracture X-ray and CT examination diagnosed Schatzker type II-IV tibial plateau fracture patients
- (2) sign the informed consent form

- (3) age from 18 to 80 years

4.2 Exclusion criteria

(1) excluding open fractures, pathological fractures, immunodeficiency, hematological diseases and severe hepatorenal disorders

- (2) refusing to sign informed consent form

4.3 Exit criteria

The patients were lost, half-way to quit and other unpredictable problems

5. Project design

5.1 Project process

A randomized controlled trial design study using the research methods:

1) After signed the informed consent, a complete medical history, vital signs and detailed physical examination were performed, and patients who met the inclusion criteria who did not meet the exclusion criteria were randomly assigned to study.

2) Patients were enrolled and randomized into groups. The arthroscopically assisted balloon expandable tibial plateau in the experimental group and the control group were treated by traditional Open Reduction and Internal Fixation.

3) Experiment group: preoperative preparation: patients with continuous epidural anesthesia, supine, conventional arthroscopic approach to the patient's joint cavity to carefully check the articular cavity hemorrhage removed, explored the meniscus and before and after cruciate ligament and collateral ligament. If there is damage, try to repair first. Step 1: If there is splitting of the tibial plateau, then make an incision in the appropriate part of the proximal tibia according to the fracture type and make a small knee transverse incision in the proximal end of the incision. The first use of minimally invasive surgical techniques in the surgical incision site to place the appropriate specifications of the locking support plate, the bottom of the plate screw holes pre-placed in a temporary cortical bone screw plate can be used in the expansion of the balloon as the outer cortex support structure, prevention of cortical rupture. The temporary fixation of cortical bone screws allow the latter to adjust the height of the plate as needed, and place two Kirschner wires on the anterior and posterior sides of the lower part of the collapsed platform to obstruct preparation for subsequent surgical procedures. Step 2:C arm fluoroscopy positioning and placement of 3 Kirschner wires, the plane formation was located at the center of the platform collapse position below the support point, as

balloon dilatation, select the appropriate balloon needle angle, guided by fluoroscopy, placed in the center of the balloon platform collapse, so that it is in the best position, filling device of bone cement injected with bone cement after expansion, at the same time the use of arthroscopy intervention on the articular surface, prevent the reduction of the articular surface is not complete, not smooth or excessive. Then Insert the other screws, suture the incision. If the tibial plateau does not splitting, the procedure should be carried out directly, and the collapsed articular surface of the tibial plateau can be restored directly.(step 2). A detailed record of 20 case of the operation time (min), the amount of bleeding(ml), postoperative pain score (visual analogue score (VAS)), the postoperative knee joint space width (mm), hospitalization time after operation (d), fracture healing time after operation (m), postoperative maximum articular surface collapse height (mm), the percentage of the restoration of joint collapse area (%),the knee joint Rasmussen scores change after surgery (Rasmussen score), failure rate and complications.

4) Control group: under the condition of random grouping, the patients in the control group were treated with traditional Open Reduction and Internal Fixation of the tibial plateau fracture. A detailed record of 20 case of the operation time (min), the amount of bleeding(ml), postoperative pain score (visual analogue score (VAS)), the postoperative knee joint space width (mm), hospitalization time after operation (d), fracture healing time after operation (m), postoperative maximum articular surface collapse height (mm), the percentage of the restoration of joint collapse area (%),the knee joint Rasmussen scores change after surgery (Rasmussen score), failure rate and complications.

5.2 Screening period (from admission to day before surgery)

- 1) come to our hospital after injury, meet the inclusion criteria.
- 2) at least 2 permanent investigators confirm the type of fracture by X-ray or CT examination.
- 3) after signed the informed consent form, according to random table method, the patients were randomly divided into experimental group or control group for corresponding treatment.

5.3 During the study period (from the day of surgery to 1 years after surgery)

- 1) the day of surgery recorded in detail the surgical procedures, operation time, intraoperative blood loss were recorded.
- 2) from operation day to leave hospital day(up to 2 weeks),the postoperative pain score, postoperative knee gap width, postoperative hospital stay days were recorded.
- 3) the patients were followed up after leave hospital: make a detailed record of the knee joint Rasmussen scores change after surgery (Rasmussen score) (1,2,3,4,6,12 months after surgery), The

percentage of joint area recovered after operation where was satisfactory, postoperative fracture healing time, maximal postoperative articular surface collapse height, postoperative failure rate and related complications.

5.4 The end of the study period (the end of the follow-up to the project end)

1. sort the appropriate information, through epidemiological or statistical experts guidance, experimental group and control group data analysis, using SPSS 22.0 statistical software analysis, measurement data to sx, using t test, counting data Percentage, using χ^2 test, $P <0.05$ for the difference was statistically significant, and use RevMan software to draw the relevant charts.
2. based on the data and charts after treatment, organize clinical discussions and experience of relevant personnel: 1.the actual operation of the new technology found in all aspects of the existing shortcomings and explore ways to improve the arthroscopic balloon dilatation tibial angioplasty, and improve the clinical diagnosis and treatment of fractures related to our hospital level. 2 through get the follow-up data under this new technology to enrich our hospital clinical data resources.
- 3 According to the results of the comparison, comparative analysis of Arthroscopic Assisted Balloon Tibioplasty and traditional Open Reduction and Internal Fixation for reduction of articular surface of tibial plateau and joint function recovery clinical curative effect, to guide the clinical work, and output clinical practical guidance and industry recognized research results for clinical decision-making and diagnosis and treatment guidelines provide a scientific basis.

6. Efficacy evaluation index

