6.1 The main efficacy indicators

Operation time (min)

Postoperative hospital stay (d) (first day after surgery to discharge day, up to 4 weeks)

Postoperative knee function Rasmussen score changes (1, 2, 3, 4, 6, 12 months)

6.2 secondary efficacy indicators

Intraoperative bleeding (ml)

Postoperative pain score (visual analogue scale (VAS)) (first postoperative day to discharge day, maximum 2 weeks)

Postoperative fracture healing time (m) (discharged to fracture healing, maximum 1 year)

Postoperative knee gap width (mm)

Postoperative articular surface maximum collapse height (mm)

Height of well-resumed postoperative articular area as a percentage of collapse area (%)

7. Safety evaluation

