8.1 Data selection for statistical analysis

Totally analyzed data sets (FAS): all randomized, grouped, and postoperative studies were performed with a complete analysis set. For the therapeutic data that failed to be observed in all treatments, the final measured efficacy data was used as end point data for analysis.

PPS (PPS): contained in the FAS, met the inclusion criteria, does not meet the exclusion criteria, no major protocol violations, and has completed the treatment period of efficacy evaluation, good compliance cases, this study constitutes with the scheme set.

Safety analysis data set (SS): all patients who were randomized to receive research methods and had postoperative safety evaluation data constituted the safety analysis data set of this study.

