8.2 Statistical analysis plan

There was no significant difference in age, gender, fracture type and other aspects between the two groups ($P>0.05$). Through epidemiological or statistical expert guidance, the experimental group and the control group data were analyzed using SPSS 22 statistical software, the measurement data in SX, using t test, count data expressed as a percentage, using X - test, $P < 0.05$, the difference has statistical significance, and draw the relevant charts with RevMan software.

9. Data management and statistical analysis

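### Appendix I schedules HSS scores where the text makes the Rasmussen score the functional outcome (the abstract's only primary), and none of the six Rasmussen visits is named as the primary comparison

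*Combined protocol and SAP*

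**What the plan says.** **Instrument.** The abstract's single Primary Outcome Measure is "the knee joint Rasmussen scores change after surgery [Time Frame", with this timing: "Time Frame: 1、2、3、4、6、12mouth Rasmussen scores change after surgery". Section 5.1 asks for it in both arms, ending its list of records with "the knee joint Rasmussen scores change after surgery (Rasmussen score), failure rate and complications". Section 5.3 says to "make a detailed record of the knee joint Rasmussen scores change after surgery (Rasmussen score) (1,2,3,4,6,12 months after surgery". Section 6.1 includes "Postoperative knee function Rasmussen score changes (1, 2, 3, 4, 6, 12 months".

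Appendix I, the trial flow chart, has no Rasmussen row. Apart from the VAS pain row, its only patient score is a row labelled HSS scores, ticked in eight columns: up to discharge, at 1, 2, 3, 4, 6 and 12 months, and at V2. HSS is not in the abbreviation list, the outcome lists or the appendix notes.

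**Analysis.** Section 8.2 specifies "the measurement data in SX, using t test, count data expressed as a percentage, using X - test" with a 0.05 threshold, and section 5.4 says the same. Neither names a visit, a repeated-measures model or a multiplicity rule. For patients with incomplete data, section 8.1 says "the final measured efficacy data was used as end point data for analysis".

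**Primary set.** Section 6.1 lists three main indicators: operation time, postoperative hospital stay and the Rasmussen score. The abstract puts operation time fifth among its secondary outcomes and hospital stay sixth: "6.the postoperative hospital stay days".

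**The concern.** Two things that should be fixed before the first patient is treated are left open.

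The first is which score is recorded. Staff who work from the flow chart would find HSS at each follow-up visit and no prompt for Rasmussen. A visit-specific score that was not recorded at its visit may not be recoverable later.

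The second is which comparison decides the trial. With six visits, one t test available at each and no visit named, the deciding visit could be chosen after the data are seen. Section 6.1 widens the choice with two further main indicators. Section 5.4 intends the results to inform clinical decisions and treatment guidelines, so a primary conclusion that depends on a later choice among visits would matter.

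There is a related gap in definition. The outcome is called a change, but no reference value is given, and neither section 5.2 nor Appendix I schedules a preoperative knee score.

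**Working it through.** **Step 1: the places that name a knee score, side by side.**

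| Place | Score | Timing |
|---|---|---|
| Abstract, primary outcome | Rasmussen | 1, 2, 3, 4, 6, 12 months |
| 5.1, both arms | Rasmussen | none given |
| 5.3 | Rasmussen | 1, 2, 3, 4, 6, 12 months |
| 6.1 | Rasmussen | 1, 2, 3, 4, 6, 12 months |
| Appendix I | HSS | to discharge, the same six visits, V2 |

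Four places agree on Rasmussen and the schedule differs. The HSS row is also ticked before discharge and at V2, where the text sets no Rasmussen assessment, so it is not plainly the same assessment under another label.

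**Step 2: inputs for the size of the visit problem.**
- From the documents: 20 per arm (3.3), t test and P<0.05 (5.4, 8.2), six visits (abstract, 5.3, 6.1).
- Assumed, because the documents do not say: two-sided tests, and the correlation of the score between visits.

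The plan states no error rate for the primary outcome as a whole, so there is no figure of its own to reproduce.

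**Step 3: chance of at least one P<0.05 across six visits when the arms do not differ.**

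Independent visits: 1 − 0.95^6 = 1 − 0.735 = 0.265, or 26.5%.

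Correlated visits, by simulation (20 per arm, pooled t test, critical t = 2.024 on 38 df):

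| Between-visit correlation | Same for every pair of visits | Fading with visit order (value is for adjacent visits) |
|---|---|---|
| 0.9 | 11% | 14% |
| 0.7 | 17% | 20% |
| 0.5 | 21% | 24% |
| 0.3 | 24% | not run |

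One pre-named visit gives 5%. Even at a correlation of 0.9 the any-visit rate is about twice that.

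**Step 4: if section 6.1 is taken at its word.** Six Rasmussen visits plus operation time plus hospital stay make eight tests. If independent: 1 − 0.95^8 = 1 − 0.663 = 0.337, or 33.7%. With visit correlations of 0.9 to 0.3, and the two added outcomes taken as independent, simulation gives about 20% to 32%.

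**The case against.** **Appendix I is not a complete collection list.** It has no row for hospital stay, which 5.1, 5.3 and 6.1 all require. Section 5.1 orders the Rasmussen score in both arms, and the data go on a case report form that is not in the documents. HSS is never spelled out, so even calling it a knee score is an inference. This stands. A reader might infer that the primary outcome will not be collected; the documents do not support that. They show a conflict that staff would have to resolve for themselves.

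**The plan can be read as pointing to the last visit.** Section 8.1 makes the final measured value the end-point value for incomplete cases, the study period ends at one year, and a completer's final value is the 12-month one. This is a fair reading, but 8.1 names no visit and its rule could equally be applied visit by visit. The gap narrows without closing.

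**Nothing tells the analyst to accept any significant visit.** Correct. A reader might take 11% to 26.5% as the trial's false-positive rate. It is the rate under one way of using the freedom that the plan leaves.

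**Naming one visit is not the only remedy.** A reader might also infer that one visit always costs less power than a Bonferroni adjustment over six. That does not hold. One visit at 0.05 detects 0.91 SD with 80% power. Bonferroni with success at any visit, and an equal true effect at all six, needs about 1.01, 0.89, 0.80 and 0.73 SD at correlations of 0.9, 0.7, 0.5 and 0.3. The ranking reverses within the assumed range, so the case for one comparison rests on clarity, not on power. One repeated-measures contrast would serve equally well.

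**Conclusion.** The point holds, and should be settled before analysis. The schedule contradicts the text on the instrument for the abstract's only primary outcome, no primary visit is named, and the abstract and 6.1 disagree on which outcomes are primary. These three findings come from comparing the text and rest on no assumption.

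The size is conditional. If P<0.05 at any one of the six visits were read as the primary result, the false-positive chance would be about 11% to 24% at correlations of 0.9 to 0.3, and 26.5% with independent visits, against 5% for one pre-named test. This assumes those correlations and two-sided tests, with the plan's 20 per arm.

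The missing reference for change is a lesser gap. The text could mean the postoperative score compared between arms or recovery over time, and the authors should say which.

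**What to change.** 1. **Appendix I:** replace the HSS row with a Rasmussen row at 1, 2, 3, 4, 6 and 12 months. Alternatively, add a Rasmussen row, keep HSS, and list HSS as a secondary outcome in the abstract and 6.2. Check that the case report form agrees.
2. **Abstract, 6.1 and 8.2:** name one primary comparison. It can be the between-arm difference in Rasmussen score at one stated visit (for example 12 months, which fits the final-value rule in 8.1) or one repeated-measures contrast. Make the remaining visits secondary.
3. **6.1 and abstract:** reconcile them so that both list the same single primary outcome.
4. **Meaning of change:** state the reference value, or call the outcome the postoperative score, since no preoperative score is scheduled.

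**Cost:** one schedule row, a check of the case report form, and wording in a few sections. No extra visit or patient is needed. The other visits lose primary status and, if the abstract is followed, operation time and hospital stay lose main status in 6.1.
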